^P At these times 18 and 30-mo postoperatively, these are phone call “visits” only with no questionnaires or exam. However, the coordinator will phone the participant to query and document: (a) if she has symptoms of a bulge or, “something falling out that you can see or feel in your vaginal area”; (b) she has had treatment for pelvic organ prolapse since the last visit date; (c) she is experiencing new medical problems or complications; (d) she has been hospitalized, had surgery, been to the emergency department, or visited a doctor for urologic or gynecologic conditions since the last visit date; and (e) she has had any change in her medications. A reminder of the next in-person study visit is also given.

Randomization & Blinding: SAS V9.3 will be used to generate stratified randomization lists using a permuted block factor of size 4 and 6. Patients will be stratified by site, hysterectomy status, and duration since menopause (<10 & ≥10 years). The randomization lists will be distributed to each site’s research pharmacy. Outcome assessors and patients will be blinded to assignment.

Standardization of surgical procedure: All patients will undergo either a uterosacral ligament suspension (“USLS”) similar to that described by Shull⁷⁶ or a unilateral sacrospinous ligament fixation (“SSLF”) in the same fashion described previously⁶⁸ as an inpatient surgical procedure under general anesthesia; these will align with a prior NICHD-sponsored Pelvic Floor Disorders Network (PFDN) surgical trial⁶⁸ with agreement on placement and type of sutures: if USLS, 1-2 permanent sutures and 1 delayed absorbable suture are placed bilaterally (i.e., 4-6 total) beginning at or above the level of the ischial spine, with the delayed absorbable suture caudad and the permanent monofilament suture(s) ~1 cm cephalad. If the SSLF is selected, 2 permanent and 2 delayed absorbable sutures (4 total) are placed unilaterally in the sacrospinous ligament. Based on level I evidence, *neither USLS nor SSLF is superior to the other for anatomic, functional, or adverse event outcomes.*⁶⁹ Participating study surgeons must have performed ≥20 of each vault suspension procedure with ≥5 in the 12 months before subject enrollment. Anterior/posterior colporrhaphies, vaginal hysterectomy, and midurethral slings are allowed *but not transvaginal mesh* for prolapse.

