6.2.3 Follow-up Visits

Preoperative Visit (within 2wk of Surgery):

- Medication Review (**Form 05**): *updated from Baseline*
- Medication Calendar documentation (**Form 07**) of study drug use Baseline-to-Pre-op
- Pelvic Floor Disorder (PFD) Questionnaires (**Form 10**)
- Preop Visit and Physical Exam (**Form 12**): assesses for any possible complaints or complications related to study cream application and re-assesses levator muscle tone and strength, and investigator assessment of vaginal atrophy Vaginal Maturation Index (VMI) for “Surgery” time point *may* be collected at this visit if it falls within 7 days of surgery.
- Adverse Events (**Form 09**) and Protocol Deviation (**Form 21**): as needed

Surgery/Hospitalization:

- Surgeon’s Report (**Form 13**): confirmation of VMI collection, investigator assessment of atrophy, surgeon assessment of tissue quality, confirmation of prolapse repair per protocol or reasons for deviation from protocol (if any), intraoperative complications.
- Hospitalization (**Form 14**): days hospitalized, bladder voiding status at discharge, immediate postoperative complications
- Return of study drug (Tube #1) and dispensation of Tube #2 is documented (**Form 07**). Tube #2 is dispensed to the subject with instructions to resume twice-weekly use once discharged home. The weight of Tube #1 is documented

and the tube appropriately disposed/destroyed.

- Medication Calendar (**Form 07**) documenting use of Tube #1 (Baseline-to-Surgery) is collected (if not already completed at Pre-op).
- Vaginal wall biopsy: an optional small full-thickness biopsy (triangle approximately 1.5x1 cm) will be obtained from the apical/ cephalad anterior vaginal wall (shown in figure below from an abdominal perspective). This is tissue that ordinarily would be discarded in the course of an anterior vaginal wall repair (colporrhaphy) procedure. This will be placed in buffered solution (RNAlater®). A preprinted barcode label with a Specimen ID is affixed. This is stable when stored at 4°C. It is shipped to UTSW on cold packs for later histologic assessment and qPCR for mRNA testing. Tissue collected locally at UTSW will initially be delivered for processing to the lab in phosphate-buffered saline (PBS), allowing additional analysis by zymography (protease enzyme activity), immunoblotting, and hydroxyproline assay for cross-linked collagen content.

[figure not shown]

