9.2 Sample Size and Randomization

The literature reports failure by the above definition occurring in ~40% of patients with a native tissue USLS (i.e., ~60% “success”).⁶⁹ A 2-sided logrank test with an overall sample size of **188 subjects** (94 each group) achieves 80% power at a 0.05 significance level to detect a hazard ratio of 0.5188 when the proportion of those "surviving" (i.e. "successes") in the control group is **65% compared to 80%** in the treated group, **measured at 1 year**. This presumes the accrual pattern across the study time period (3 years of accrual) is uniform. This N=188 already accounts for **25%** either lost to follow-up *or non-adherent to study cream* in the control and treatment groups. Allowing for an additional **15% loss of participants** from baseline to surgery, **222 total participants** are needed.

Potential problems & alternatives:

Differences in baseline characteristics between the groups may occur by chance, but we will mitigate that risk by stratifying by clinical site, hysterectomy status, and duration since menopause (<10y & ≥10y).

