9.2.1 Treatment Assignment Procedures

A randomized, double-blind, placebo-controlled trial design (CE cream versus placebo) will be used in this study. SAS V9.3 will be used by the study biostatistician to generate the stratified, randomization lists. Patients will be stratified by site, hysterectomy status, and duration since menopause (<10 and ≥10 years). The randomization lists will be distributed to each site’s research pharmacy (or their designee). Those conducting the primary and secondary measurements as well as the patients will be blinded to treatment assignment. These data will *not* be housed in study’s database (i.e. REDcap®).

At the discretion of the primary investigators at any of the clinical sites, they may request the primary site PI to have the blind broken. The primary site PI—likely in consultation

with the Safety Monitor, as needed—will then request this information of the DCC study database manager (permitting [name] to remain blinded) if it is clinically needed to understand the medication that the patient is receiving. It is anticipated that this would only be requested for important medical reasons, e.g., a serious adverse event or significant allergic reaction to study cream. In most cases, patient skin irritation with cream application could prompt discontinuation of the study medication without unmasking. There is no plan for clinical site research pharmacists to unmask participants, research coordinators, or local site PIs directly. Planned breaking of the randomization codes will only be after all participants have reached the primary study outcome time point one year postoperatively; there are no plans for interim/ early data analyses.

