Atrophy (and its resolution, **Subaim 2d**) will be queried at baseline, Pre-op, 6- and 12-mo postoperatively using standardized questions about bother related to vaginal dryness, irritation/itching, soreness/pain, discharge, and dyspareunia (if sexually active); these symptoms are each scored as 1=not at all, 2=somewhat, 3=moderately, or 4=quite a bit bothersome.⁷⁵ The most bothersome symptom (MBS) is also queried. On exam, a modification of the vaginal health composite score⁸⁵ will have the examiner grade vaginal mucosal dryness, pallor, presence of rugae, and presence/absence of petechiae. The vaginal maturation index objectively categorizes percent of superficial, intermediate, and parabasal cells to be used as an index of patient adherence and to examine for correlation with symptom bother from other PFDs.

Aim 3: Quantify histomorphology and connective tissue homeostasis of the vaginal wall in postmenopausal women with symptomatic prolapse undergoing surgical repair with or without pre- operative intravaginal estrogen therapy.

Aim 3 Methodology:

a. Vaginal wall biopsy: Standardized full-thickness anterior apical vaginal wall biopsies will be obtained from all consenting participants at the time of prolapse repair. Biopsies from secondary clinical sites will be received in RNA preservative (RNAlater®). Although this buffer is excellent for preservation of RNA and facilitates dissection of biopsy material into various tissue components (e.g., muscularis from mucosa) and fixation of tissues after receipt, immunoblot analysis and enzymes assays are not possible. Thus, tissues obtained from only the primary site (UTSW) will be used to quantify protein and enzyme activity in addition to molecular analysis. Biopsies from all sites will be used for molecular and histopathology analyses.

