Molecular profile of vaginal wall tissues (all clinical sites). High quality RNA from tissue samples obtained in this trial will facilitate a comparative analysis of gene expression related to matrix synthesis and degradation. It is not possible to analyze hundreds of genes involved in these pathways especially in ~392 (196 ea of muscularis and mucosa) tissues. We, therefore, choose to quantify mRNA levels of select genes related to matrix synthesis and degradation to determine a molecular profile of estrogen action in vaginal tissues.

Analysis of tissues from women enrolled in our pilot trial indicated that, of 7 genes important in collagen and elastin synthesis, the magnitude of estrogen-induced change was greatest and most consistent in *Col1a1* (6-fold). With increased numbers of subjects, we expect that vaginal estrogen will also result in increased *LOX* gene expression (which correlates with enzyme activity) in the vaginal muscularis. Hence, we will utilize qPCR to measure relative levels of *LOX* and *Col1a1* mRNA as markers of collagen synthesis in all tissue samples from this trial. *Col3* and *tropoelastin* will be used as potential negative controls and at least two housekeeping genes will be used as normalizers (*h36B4* and *GAPDH*).

Our pilot trial indicated that mRNA levels for serine protease and MMP inhibitors were not regulated by vaginal estrogen. The single exception was the serine protease inhibitor, *α 1-antitrypsin*, which tended to be increased in mucosal samples from women treated with estrogen ($P=0.27$). In contrast with protease inhibitors, 2 protease genes (*MMP1* and *MMP12*), were significantly decreased in tissues from CE-treated women, and MMP9 activity was also downregulated dramatically in CE-treated women. Thus, *MMP1*, *MMP12*, and *α 1-antitrypsin* will be quantified in all tissue samples using *MMP2* and *TIMP1* as negative controls.

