Aim 3 Outcomes: If there is 10% loss of patients from randomization (baseline) to surgery, there will still be 100 patients per arm eligible for the standardized intraoperative apical anterior vaginal wall surgical biopsy. Our pilot trial (Section 2.2a, *Humans*) indicates sufficient power to determine 2-fold differences in collagen subtypes and MMP activity using tissues from UTSW. Further, with ~42 samples from UTSW (21 in each group), this will provide 80% power to also detect 2-fold differences in LOX protein and mRNA expression. All Aim 3 outcomes of interest (e.g. histological wall thicknesses, qPCR-determined relative mRNA levels, collagen subtypes and elastic fiber content, collagenase and protease activity) will be summarized using the following statistics: mean, standard deviation, median, minimum and maximum. Additionally, because most biomarkers are not normally distributed, the geometric mean and standard deviation based on natural log transformed values will also be calculated. Summaries will be constructed by treatment group (CE vs. placebo) and comparisons conducted using 2-tailed Student’s *t*-tests comparing natural log transformed levels. Because this translational study (Aim 3) is considered to be descriptive and a relatively large number of markers are being considered, all p-values will be presented without adjustment for multiple comparisons and should be interpreted accordingly. We will correlate any treatment-group differences in vaginal wall or smooth muscle histomorphology, ERs, collagen gene expression, and protease downregulation with *clinical outcomes*, namely, objective or subjective “success” as outlined in Aims 1 and 2.

Ideally, CE cream application will support an improvement in prolapse recurrence success/failure rates 1y postop, but even if CE cream has a null or non-significant effect, the entire population will be divided into prolapse repair failures (*cases*) and successes (*controls*), and, controlling for CE cream exposure, univariate comparisons will be made of the continuous outcomes from Aim 3 (2-tailed Student’s *t*-tests). Those variables that attain a significance level of 0.1 or less in univariate analyses will be considered jointly in a multivariable backward stepwise logistic regression model. An accepted “rule of thumb”

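### Aim 3 compares arms on pooled three-site tissue with an unadjusted t-test; if site shifts a marker, precision is lost, and adding the randomisation factors would recover it

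*Combined protocol and SAP*

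**What the plan says.** Section 9.5 (Aim 3 Outcomes) gives the between-arm test: "Summaries will be constructed by treatment group (CE vs. placebo) and comparisons conducted using 2-tailed" Student's t-tests of natural-log levels. It names no covariate. It also calls Aim 3 descriptive and leaves p-values unadjusted for multiplicity.

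Section 9.2.1 gives the design: "Patients will be stratified by site, hysterectomy status, and duration since menopause". The randomisation paragraph of Section 3 adds that lists are generated "using a permuted block factor of size 4 and 6".

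The Aim 3 methodology in Section 9.4.2 sets out which tissue is used:
- "Biopsies from all sites will be used for molecular and histopathology analyses". *LOX* and *Col1a1* mRNA are to be measured "as markers of collagen synthesis in all tissue samples from this trial".
- By contrast, "tissues obtained from only the primary site (UTSW) will be used to quantify protein and enzyme activity".

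Handling differs by site. Section 9.4.2 has the two secondary sites send tissue in RNAlater. Section 6.2.3 (Surgery/Hospitalization) has the primary site do otherwise: "Tissue collected locally at UTSW will initially be delivered for processing to the lab in phosphate-buffered saline (PBS").

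Elsewhere in Section 9.5, the Subaim 2d analysis of covariance does include study center as a factor.

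**The concern.** Stratified blocks keep the arms close to equal within each site, so a marker that runs higher or lower at one site adds little to the arm difference. A pooled two-sample t-test does not use this. It counts the between-site spread as noise, and its standard error then overstates the real variability of the arm difference.

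The plan offers a concrete reason to expect some site shift: the transport medium changes at the boundary between UTSW and the other two sites. What is at stake is the precision of the mRNA and histology comparisons and the ability to see modest estrogen effects. Section 9.5 also carries treatment-group differences forward to be correlated with clinical outcomes, so a missed difference could drop out of that step.

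**Working it through.** **Plan figures first.** Section 9.5 expects 100 biopsies per arm after 10% loss: 111 × 0.9 = 99.9, which agrees. It states 80% power with 21 per group for a 2-fold difference in LOX. No log-scale SD or alpha is given for Aim 3, so this cannot be reproduced independently. With a two-sided 0.05 level (assumed), the SD it implies is ln 2 / [(1.960 + 0.842) × √(2/21)] = 0.693 / (2.802 × 0.3086) = 0.80, or 0.78 by the noncentral t. That statement concerns UTSW tissue alone, so a site term does not alter it.

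**Effect on the pooled test.** Let R² be the share of log-marker variance explained by site. With exact balance within site, the t-test's standard error exceeds the true one by the factor 1/√(1 − R²), and the actual size of a nominal 5% test is 2[1 − Φ(1.96/√(1 − R²))]. For R² = 0.2 these are 1/√0.8 = 1.118 and 2[1 − Φ(2.191)] = 2.8%.

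Biopsy is optional, so balance is not exact. The simulation therefore used 222 women, 12 strata (3 × 2 × 2), blocks of 4 and 6, and biopsies missing at random, with 6,000 runs per setting. Assumptions: equal site sizes, UTSW differing from the other two sites, and no treatment effect.

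| Site R² (assumed) | SE ratio, exact balance | SE ratio, 10% missing | SE ratio, 30% missing | Size of t-test, 10% missing | Size with site in model, 10% missing |
|---|---|---|---|---|---|
| 0 | 1.00 | 1.00 | 0.99 | 5.0% | 4.9% |
| 0.1 | 1.05 | 1.06 | 1.03 | 3.9% | 4.8% |
| 0.2 | 1.12 | 1.09 | 1.07 | 3.3% | 4.8% |
| 0.3 | 1.20 | 1.17 | 1.12 | 2.2% | 4.7% |

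The SE ratio is the mean t-test standard error over the true SD of the arm difference. The excess grows with R² and shrinks as more biopsies go missing.

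**What this means for power.** Assume UTSW supplies 42 of 196 women (Section 9.5 gives about 42 UTSW samples, Section 9.4.2 gives 196 women), 98 per arm, within-site SD 0.78 and exact balance. The between-site variance for a site shift of f-fold is p(1 − p)(ln f)², with p = 42/196 = 0.214. For f = 2 it is 0.1684 × 0.4805 = 0.081, and the site share is 0.081/(0.081 + 0.608) = 12%. Power is Φ(ln θ/SE − 1.96k), where θ is the true fold difference, SE = 0.78 × √(2/98) = 0.1114, and k = √(total/within variance).

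| Site shift (assumed) | Site share | k | Power, θ = 2 | Power, θ = 1.5 | Power, θ = 1.35 |
|---|---|---|---|---|---|
| none, or site in model | 0% | 1.00 | >99.9% | 95% | 77% |
| 1.5-fold | 4% | 1.02 | >99.9% | 95% | 75% |
| 2-fold | 12% | 1.06 | >99.9% | 94% | 73% |
| 3-fold | 25% | 1.15 | >99.9% | 92% | 67% |
| 4-fold | 35% | 1.24 | >99.9% | 89% | 61% |

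Only the 2-fold difference is the plan's own. The 1.5 and 1.35-fold effects are illustrations. Because exact balance is assumed, the losses shown are upper figures for each shift.

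**The case against.** The strongest reply is that nothing here is broken. The t-test stays valid, and its error is on the safe side. Aim 3 is labelled descriptive. At the 2-fold difference that Section 9.5 targets, power on the pooled tissue is above 99.9% with or without a site term. The pilot changes in Section 2.2 were larger still (6-fold for *Col1a1* mRNA, 2.7-fold for muscularis thickness). All of this stands, and it limits the importance of the point.

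The size is also uncertain. No site shift is reported. Section 9.4.2 normalises mRNA to at least two housekeeping genes, which may remove part of a handling effect, and nothing in the documents says that the transport medium changes measured wall thickness. Within-site balance is only approximate, because biopsy is optional and Section 10.1 describes it in women undergoing vaginal hysterectomy. These points make the claim conditional and smaller; they do not reverse its direction.

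A reader might go further and infer that the Aim 3 standard errors are too wide as a matter of fact, or that Aim 3 is underpowered. The documents support neither. The first needs a site effect that they do not report. The second is contradicted by the power at the plan's own target, and the stated 80% rests on single-site tissue.

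The descriptive label does not settle the matter. Section 9.5 uses it to explain the lack of multiplicity adjustment, which is a separate question from whether the analysis reflects the design. Subaim 2d already includes center.

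**Conclusion.** The point holds in a limited, conditional form. For mRNA and histology markers pooled over three sites, the unadjusted t-test ignores the factors used to randomise. If site explains 10% to 30% of log-scale variance, its standard errors are about 6% to 17% too wide with 10% of biopsies missing, or 3% to 12% with 30% missing. The nominal 5% test then has a true size of 3.9% to 2.2% in the 10% case. The variance shares and equal site sizes are assumptions.

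The consequence is lost precision and some lost power for effects well below 2-fold. The primary outcome is untouched. For UTSW-only protein and enzyme assays a site term changes nothing, although the other two stratification factors are ignored there too. This is a modest improvement that is worth making because it costs almost nothing.

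**What to change.** In Section 9.5, Aim 3 Outcomes, replace the between-arm t-test with a linear model on the natural-log level of each marker. Include treatment, site, hysterectomy status and menopause duration (<10 or ≥10 years) as main effects. For protein and enzyme assays done on UTSW tissue only, omit site and keep the other two factors. Report each result as a ratio of geometric means (CE to placebo) with its 95% CI. If every biopsied woman falls in one hysterectomy category, that term drops out.

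The cost is one or two sentences of text and four degrees of freedom for pooled markers (196 − 6 = 190 residual, against 194 for the t-test), or two for UTSW-only assays (42 − 4 = 38, against 40). No extra data are needed, since all three factors are recorded at randomisation.

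### The 67-failure, 7-variable basis for the biomarker model of repair failure does not hold once a marker measured only at UTSW enters it, and the all-site comparison has no site term

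*Combined protocol and SAP*

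**What the plan says.** Section 9.5 (Aim 3 Outcomes) states that "the entire population will be divided into prolapse repair failures (*cases*) and successes (*controls", and that "univariate comparisons will be made of the continuous outcomes from Aim 3" with control for estrogen-cream exposure. It lists the Aim 3 outcomes as including "qPCR-determined relative mRNA levels, collagen subtypes and elastic fiber content, collagenase and protease activity". Variables reaching P of 0.1 or less are then considered jointly in a backward stepwise logistic model. Its size is justified by 67 failures (40% of 222 participants after 25% loss) and a rule of 10 failures per degree of freedom, from which the plan concludes that at least 7 variables can be analysed.

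Section 9.4.2 (Aim 3 Methodology) says that for tissue received in RNAlater "immunoblot analysis and enzymes assays are not possible", so that "tissues obtained from only the primary site (UTSW) will be used to quantify protein and enzyme activity in addition to molecular analysis". By contrast, tissue from every site goes to molecular and histopathology work. The footnote to the design schema in section 3, and section 6.2.3, add the hydroxyproline assay for cross-linked collagen to the list done only on local tissue. Section 9.5 bases its power statement for that site on about 42 samples, 21 per group.

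Handling also differs: "Tissue collected locally at UTSW will initially be delivered for processing to the lab in phosphate-buffered saline (PBS", whereas the other two sites ship in RNAlater. Study center is a named factor for Subaim 2d in section 9.5, but not for the failure-versus-success analysis.

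**The concern.** The event count that justifies the model is an all-site count, while a large class of the candidate markers exists at one site only. The plan has no rule for markers missing by site. The imputation wording in section 9.5 concerns missing follow-up points, not assays that cannot be run at two of three sites. Standard logistic software would drop every woman from the other two sites as soon as one UTSW-only marker was in the candidate set.

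This is a realistic prospect. In section 9.4.2 the investigators propose that failed repair will be associated with raised markers of collagenase and elastase activity. Activity assays of that kind are the ones limited to UTSW, so if the hypothesis is right, these markers should tend to pass the screen.

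The second issue concerns markers that are measured everywhere. Site is a randomisation stratum, so site and handling are balanced between estrogen and placebo. Nothing balances them between failures and successes. If handling shifts a marker and one site has more failures, the marker can appear to predict failure with no true relationship.

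At stake is the statement in section 9.5 that the analysis will identify biomarkers predicting failure, with a possible use in choosing the surgical approach.

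**Working it through.** **1. The plan's own figure.** Inputs from section 9.5: 222 participants, 25% loss, 40% failure.

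- Failures = 222 × 0.75 × 0.40 = 66.6, which reproduces 67.
- Predictors at 10 events each = 67 / 10 = 6.7. This rounds to the stated 7; a strict reading gives 6.

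**2. The same rule when a UTSW-only marker is in the model.** Inputs: about 42 UTSW samples (section 9.5), complete-case fitting (assumed, since the plan names no alternative).

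- Share of tissue: 42 / 196 = 21%, taking the 196 women implied by the tissue count in section 9.4.2.
- At 40% failure: 42 × 0.40 = 16.8 failures; 16.8 / 10 = 1.7, so 1 whole predictor. The estrogen-exposure term would use it.
- At 27.5% failure, the average implied by 65% and 80% success in section 9.2, (35 + 20) / 2: 42 × 0.275 = 11.6 failures; still 1 predictor.
- If UTSW instead contributed a full third of 222 (74 women, an assumption): 74 × 0.40 = 29.6 failures; 2 whole predictors.

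None of these approaches 7. Postoperative loss lowers each further.

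**3. What this does to a single comparison.** The difference detectable with 80% power at two-sided 0.05, in SD units, is (1.960 + 0.842) × √(1/a + 1/b), for a failures and b successes.

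- All sites, 67 v 100: 0.44 SD.
- UTSW only, 17 v 25: 0.88 SD.

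**4. Site confounding in the all-site markers.** The documents give neither a handling effect nor failure rates by site, so every input here other than the sample counts is assumed. Simulation: 196 women, 42 from UTSW, no true marker effect, unadjusted t-test screened at 0.10, 4,000 runs per setting.

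| Handling shift at UTSW | Equal failure (40% v 40%) | 30% v 43% | 25% v 44% | 55% v 36% |
|---|---|---|---|---|
| 0 SD | 0.10 | 0.10 | 0.10 | 0.10 |
| 0.5 SD | 0.10 | 0.12 | 0.13 | 0.13 |
| 1 SD | 0.09 | 0.16 | 0.21 | 0.21 |

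Failure rates are UTSW v other sites. With a site term the rate was 0.09 to 0.10 in every cell. Milder inputs leave the unadjusted screen near nominal: a 6.5-point failure gap gives about 0.11 at 1 SD and 0.10 to 0.11 at 0.5 SD, and a 0.25 SD shift gives about 0.10 to 0.12 even with gaps of 15 to 22 points.

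**5. Budget for the all-site model.** Site (three sites) takes 2 degrees of freedom and estrogen exposure 1. From the plan's 7 this leaves 7 − 3 = 4 markers; from a strict 6 it leaves 3.

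**The case against.** The strongest reply is that the collapse is a contingency. A UTSW-only marker must pass the 0.1 screen and be taken forward, and the fit must be complete-case. The plan says that screened variables are considered jointly, not that all are forced in, and its own 10-events rule would flag an overfitted single-site model. Section 9.4.2 also has a short all-site gene list, and section 9.5 gives the UTSW subset its own power statement, so the two marker sets are already partly separated. This stands as a limit on the claim. It does not remove it, because section 9.5 never says that the failure model is confined to the all-site set, and its stated event count covers only that set.

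A reader might infer that the model must either shrink to one site or be confounded with site. The documents do not support that: a model that happened to keep only qPCR and histology markers would use all sites, and confounding needs both a handling effect and a failure gap between sites. A 1 SD shift is also large. If 21 per group gives 80% power for a 2-fold difference, the implied SD on the natural-log scale is about 0.80, so 1 SD is roughly a 2.2-fold artefact. For qPCR it would have to survive normalisation to at least two housekeeping genes. Surgery is standardised across sites, which argues against a wide failure gap.

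A reader might also apply the 25% loss to the 42 samples and quote about 13 failures. The plan applies that loss to all 222 participants, while the 42 are samples already collected at surgery, so this may count preoperative loss twice.

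Finally, Aim 3 is labelled descriptive. In section 9.5 that label excuses the absence of multiplicity adjustment; it does not address missing markers or site.

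**Conclusion.** The point holds in a conditional form. If any protein, enzyme-activity or cross-link marker enters the joint model and the fit is complete-case, the model rests on about 17 failures at the plan's 40% rate (about 12 to 30 over the alternatives tried, before postoperative loss). It then supports 1 or at most 2 predictors, not 7. This assumes that the roughly 42 samples are all the UTSW tissue available.

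The missing site term is a real gap, but the bias it might cause is of unknown size. The simulated rates show only what could happen under assumed inputs.

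The all-site figure of 67 is itself an upper figure for tissue-based work: the biopsy is optional, and section 10.1 describes biopsies in women having vaginal hysterectomy.

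Severity is minor. This is a secondary translational analysis, and no primary or Aim 2 conclusion changes.

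**What to change.** In section 9.5:

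- Limit the multivariable failure model to markers measured at all sites (qPCR and histomorphology), with site and estrogen exposure as covariates counted against the events-per-variable budget.
- State that the 67-failure, 7-variable figure applies to that model only, and falls further if biopsies are declined.
- Run the all-site failure-versus-success comparisons as linear models on the log marker, with failure status, estrogen exposure and site as terms; a two-sample t-test cannot carry the covariates.
- Analyse UTSW-only markers within UTSW, one at a time, labelled descriptive, with their own failure count reported.

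Adding site to the all-site log-scale comparisons of estrogen with placebo is optional. Randomisation was stratified by site, so it would gain precision there, not correct a bias.

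The cost is analysis wording only, with no new data or samples. Site uses two degrees of freedom, and UTSW-only markers can no longer be claimed as independent predictors of failure.
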